#### **Customized Task-Oriented Training Protocol:**

Subjects will engage in one hour of concentrated task-practice directed at the paretic arm and hand. Task-practice sessions will be structured and supervised by a trained and licensed therapist. Selection of functional motor tasks for a given subject will be derived from their baseline FM-UE score. Based upon assessment information obtained from the baseline FM-UE score, motor tasks will be selected that are optimally challenging and customized to personal abilities and goals. This method also allows for systematic progression of task types and difficulty to maintain a "just-right" match between the subject's abilities and task-difficulty. Tasks practices will address specific gross-motor, fine-motor, proximal, and/or distal movement components within the context of functional tasks. Repetition and feedback schedules and methods will follow the theoretical framework of the Task-Oriented Approach.

#### **D5. 1. Timeline:**

[figure not shown]
About 600 patients per year with a primary diagnosis of acute ischemic stroke were admitted to MUSC Stroke Center. About 12-15% patients (6 - 8 patients per month) can meet the inclusion criteria. In addition, Center of rehabilitation Science in Neurological Conditions maintains a database with 50 stroke subjects who were agreed to be contacted for future research studies, this study will also recruit from the Registry for Stroke Recovery (RESTORE-Pro#00037803), which is a registry with subjects consented for future contact. (please refer to details in D5.5). Thus, we should have no problem obtaining the required number of subjects from the **CTTR Core**. The protocol will be submitted to the MUSC IRB with expectation of final approval by June, 2013. Subject enrollment will begin immediately if the proposal is funded. We expect to complete the Aim1 in year 1 and aim 2 in year 2 (**Table 1**).

Table 1	Pre-year	Year 1				Year 2			
Quarter	1	1	2	3	4	1	2	3	4
Research Plan	Receive IRB Approval	Start recruitment for Aim1, and plan to recruit 2-3 subjects per months, complete Aim1 by the end of year 1.				Start recruitment for Aim2, and plan to recruit 2 subjects per months and complete it at the end of year 2			Start R01 proposal
Training Classes		Clinical Trial Methods Course in Neurology				Imaging tool analysis in FSL and SPM			
Scientific Meetings		Present data from Aim1 internally - Neuroscience Grand Rounds; - SCTR SOCRATES club - Monthly stroke team meetings;			International stroke conference or American Society of Neuro-rehabilitation Conference		Present data from Aim2 internally - Neuroscience Grand Rounds; - SCTR SOCRATES club - Monthly stroke team meetings;		
Publications		Manuscript#1: efficacy and safety of various current level of tDCS in stroke patients				Manuscript # 2: Optimal tDCS stimulation montage for stroke patients			

**D5. 2. Integration with COBRE:**

This proposal is well integrated into the COBRE application. It utilizes all of three scientific cores in the COBRE (**Figure**), and most importantly, the applicant has a clear plan for a next project to continuously utilize all of cores. Further, the proposed study will advance the **BSTIM Core** as it potentially leads to a new treatment for post-stroke motor recovery. Specifically, much of the study will be performed in the **QBAR Core** laboratories and a QBAR therapist will conduct the therapy session for the experiments outlined in Aim 1 and Aim 2. The **BSTIM Core** will provide the tDCS device, TMS and necessary training. The research assistant from Brain stimulation laboratory, along with the applicant; will conduct TMS assessment of cortical excitability on stroke subjects. The MR scan will be conducted at the Center of Advance Imaging Center (CAIR) where **NI Core** is

located. The **NI Core** will also provide necessary training and staff for imaging process and analysis.

The applicant already had multidisciplinary collaboration with other junior investigators in the COBRE application. For example, [name] has an established collaborative relationship with [name] whose expertise is neuro-imaging with functional MRI and cortical excitability assessment with TMS. They have collaborated on the ongoing pilot study "Bihemiespheric Stimulation and Constrained-Induced Movement Therapy to Promote Post-Stroke Motor Recovery". Part of data from this

study were used as preliminary data supporting two proposals for this COBRE application. [name] current project also provide a neurobiological basis for stroke recovery. The result from her project could be helpful for [name] to design the R01 project in planning to uncover the recovery mechanism associated with tDCS. [name] also has collaborated with [name] whose expertise is investigating rTMS as an adjunct tool for stroke recovery while [name] is studying how tDCS promote stroke recovery. tDCS and rTMS are two similar but different non-invasive brain stimulation techniques, they both have the capability to modulate cortical excitability and induce subsequent brain plasticity, currently they both hold promise for stroke motor recovery. They have been meeting regularly to trouble shoot technical aspects of the two techniques, and working together testing the new magstim® rTMS with brainsight.

### **D5.4. Applicant's Future Project (Including R01):**

This proposal serves as a critic bridging step between the applicant's prior training and his next milestone - an R01 application. The R01 is planned to submit in the end of year two when the proposed experiments are close to completion. The proposed R01 project is a Phase II single-center clinical trial to assess the efficacy of tDCS for post-stroke motor recovery with the current and stimulation montage determined from this proposal. If R01 project show promising result, [name] hope to launch a U01 project to further test the tDCS in post-stroke motor recovery in a multi-center phase III clinical trial.

### **D5.5 Additional information about recruiting patients from research database:**

Subjects with stroke will be recruited from the recruitment database maintained at the MUSC Center for Rehabilitation Research in Neurological Conditions (CRRND) which is housed in the CHP Department of Health Sciences and Research (secondary appointment of the PI and primary appointment of the research therapist). The research database (approved MUSC IRB #15991) currently contains ~200 persons with stroke who have signed informed consent and agreed to be contacted for research participation. The research

database is managed by a designated coordinator. This coordinator will be provided with the inclusion/exclusion criteria for the current study. This study will also recruit from the Registry for Stroke Recovery (RESTORE-Pro#00037803), which is a registry with subjects consented for future contact. RESTORE staff will query the registry for potential subjects and provide the Principal Investigator (PI) with the contact information of subjects who meet their criteria. The PI or research staff will contact subject to further screen for potential enrollment. When a potential participant is identified that meet inclusion criteria the PI, project coordinator or research therapist will contact participants by phone to determine if they want to participate in the current study. If they wish to participate they will be scheduled for a time for the PI, project coordinator or research therapist to obtain informed consent for the study proposed. Consent will be obtained after reviewing the protocol and consent form with each potential subject. If a potential subject is deemed unable to participate in informed consent, consent will be obtained from a relative with the patient present. For patients consenting themselves, every attempt will be made to have a relative present during the informed consent. The MUSC IRB will approve the informed consent form.

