#### **Aim 1: To determine the optimal tDCS current in stroke subjects**

The optimal current balances cortical excitability and tolerability/safety in stroke patients. We will investigate the optimal current in range of 1 mA to 4 mA. We hypothesize that 4 mA is tolerable, safe and can induce the highest level of cortical excitability in the lesional motor cortex. We will adapt the classic, gold-standard 3+3 experimental design that is commonly used to find the maximal tolerable dose in drug trials. Tolerability/safety will be investigated by monitoring clinically detectable symptoms by monitoring vital signs and surveying subjects with a questionnaire before and after stimulation, additionally by detecting subclinical neuronal injury using (1) Magnetic Resonance Imaging/Diffusion Weighted Imaging (MRI/DWI) to detect any focal ischemia; and 2) Molecular biomarkers: S100b and neuron-specific enolase (NSE) to detect neuronal injury. Cortical excitability is measured by the amplitude of motor evoked potentials (MEPs) induced by TMS from the abductor pollicis brevis muscle of the affected side.

**What is the optimal tDCS electrode montage for stimulation?** According to the theoretical model underlying the use of tDCS for stroke motor recovery, stroke causes an “interhemispheric imbalance” with decreased motor excitability in the ipsilesional hemisphere and excessive excitability in the contralesional hemisphere. This has led to studies testing the effects of anodal (excitatory) stimulation to the lesional hemisphere, cathodal stimulation (inhibitory) to the non-lesional hemisphere or combined bi-hemispheric stimulation. However, it has not been established which montage can induce the maximal cortical excitability, and eventually the maximal motor recovery.

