### **Exclusion Criteria:**

Subject who meets **any** of the following criteria will be excluded from the study.

- Primary intracerebral hematoma, or subarachnoid hemorrhage,
- Bihemispheric ischemic strokes;
- History of prior stroke or old infarct demonstrated on the CT or MRI or documented in medical records;
- Other concomitant neurological disorders affecting upper extremity motor function;
- Documented history of dementia before or after stroke;
- Documented history of uncontrolled depression or psychiatric disorder either before or after stroke which could affect their ability to participate in the experiment;
- Uncontrolled hypertension despite treatment, specifically SBP/DBP $\geq$ 180/100mmHg at baseline;
- Presence of any MRI/tDCS/TMS risk factors: a) an electrically, magnetically or mechanically activated metal or nonmetal implant including cardiac pacemaker, intracerebral vascular clips or any other electrically sensitive support system; b) non-fixed metal in any part of the body, including a previous metallic injury to eye; c) pregnancy, since the effect of tDCS on the fetus is unknown; d) history of seizure disorder or post-stroke seizure; e) preexisting scalp lesion, bone defect or hemicraniectomy.

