### **D1. 2. Recruitment Process & Procedure:**

A schedule of assessments is presented in **Table 2**.

[figure not shown]
Table 2	Baseline*	Stimulation Day (Day 0)	Follow-up
---------	-----------	-------------------------	-----------

	(Day -7 ± 7)	Pre-stim	Post-stim	(Day 14 ± 4)
Eligibility Determination and Informed Consent	X			
Demographics	X			
Vital Signs and Safety Questionnaire	X	X	X	X
TMS Evaluation	X	X	X	
Laboratory		X	X	X
Brain MRI		X	X	

\* Baseline can be same day as Stimulation Day to facilitate recruitment.

[figure not shown]
[figure not shown]
- **Baseline Day (Total Estimated Time: ~ 2 hours)**

1. Subject reports to the College of Health Professions (CHP) building QBAR laboratory.
2. Subject is consented first, then starts screening process.
3. Vital signs are taken. Urine pregnancy test for subjects of childbearing age. Estimated time is 10 minutes.
4. Demographics collected, including age, ethnicity, gender, time from stroke (in months), side of infarct, handedness, medical history and medication list. Estimated time is 20 minutes.
5. A technician from the **BSTIM Core** will perform a **Basic TMS Neurophysiological Assessment** to determine if a MEP is inducible on abductor pollicis brevis (APB) muscle on the affected side by TMS (Details in **BSTIM Core**). Estimated time is 30 minutes.
6. Subject takes structured questionnaire. The questionnaire inquires whether the patient has experienced any of the following symptoms: headache, nausea, burning, tingling, itching, neck pain, electric shock, inattention and etc. It also has open questions inquiring about subject's general impression about the stimulation. Estimated time is 10 minutes.
7. A therapist from the **QBAR Core** will perform **Clinical Assessments** including upper-extremity Fugl-Meyer (UE-FM) scale. Estimated time is 30 minutes.
8. Subjects who meet the inclusion/exclusion criteria are eligible for the study and move to the next step.

- **Stimulation Day (7 days after baseline day; Estimated Time: ~4 hours)**

9. Subject report to Center of Advance Imaging for Research (CAIR). The **NI Core** will perform **structural 3T MRI** (Details in **NI Core and MRI protocol**). Estimated time is 30 minutes.
10. Subject is transported to CHP research building QBAR laboratory (less than 100 yards away).

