11. Blood draw is performed collecting 10 ml's and specimen is sent to [name] laboratory in the Children's Hospital. . Urine pregnancy test for subjects of childbearing age. We have updated the protocol. Estimated time is 10 minutes.
12. Subject takes structured questionnaire survey. Estimated time is 10 minutes.
13. A technician from the **BSTIM Core** will perform a **Basic TMS Neurophysiological**

[figure not shown]

**Assessment** to determine cortical excitability (details in **BSTIM Core and TMS protocol**) in the BSTIM laboratory in the CHP research building (the room next door to the QBAR laboratory).

Estimated time is 30 minutes.

14. Vital signs are taken. Estimated time is 5 minutes.
15. The **BSTIM core** oversees tDCS stimulation protocol. The PI will administer the tDCS under the supervision of the **BSTIM core**.
16. Coincident with the beginning of stimulation, the therapist from the **QBAR Core** begins a one hour **Upper Extremity Rehabilitation** session of patient-targeted upper extremity function therapy (details in **QBAR Core and Therapy Protocol**). Estimated time is 60 minutes.
17. At the end of the rehabilitation session, the technician from the **BSTIM Core** will again perform a **Basic TMS Neurophysiological Assessment** to determine cortical excitability. Estimated time is 30 minutes.
18. The structured questionnaire survey is performed again. Estimated time is 10 minutes.
19. A second blood draw is performed and specimen is delivered to [name] laboratory in the Children's Hospital I. Estimated time is 10 minutes.
20. Subject is transported to CAIR. **NI Core** will again perform **structural 3T MRI** (Details in **NI Core and MRI protocol**). Estimated time is 30 minutes.
21. Patients are advised to call the study team if they experience any untoward side effect before the follow up day.

- **Follow-up day (14 days after stimulation day; Estimated time: ~ 0.5 hour)**

22. Subject reports to CHP research building QBAR laboratory.
23. A blood draw is performed collecting 10 ml's and specimen is sent to [name] laboratory in the Children's Hospital. Estimated time is 10 minutes.
24. The structured questionnaire survey is performed again. Estimated time is 10 minutes.

- **Final analyses:**

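### Aim 1 can enrol subjects on a relative's consent without requiring that they can answer the safety questionnaire, which puts symptom data and after-discharge reporting at risk

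*Combined protocol and SAP*

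**What the plan says.** **Consent.** D5.5 provides: "If a potential subject is deemed unable to participate in informed consent, consent will be obtained from a relative with the patient present". The sentence carries no cap, makes no distinction between the two aims, and is not tied to whether the subject can describe symptoms.

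**Eligibility.** The four inclusion criteria cover age and stroke history, completed rehabilitation, arm weakness, and an inducible motor evoked potential. None concerns language, comprehension or ability to respond. The nearest exclusions are "Documented history of dementia before or after stroke" and uncontrolled depression or psychiatric disorder "which could affect their ability to participate in the experiment". Aphasia is not mentioned.

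**Symptom capture.** The Aim 1 statement describes clinical tolerability as "monitoring clinically detectable symptoms by monitoring vital signs and surveying subjects with a questionnaire before and after stimulation", with MRI and two blood markers added for subclinical injury. D1.2, step 6, gives the content of the questionnaire: "headache, nausea, burning, tingling, itching, neck pain, electric shock, inattention and etc". It adds: "It also has open questions inquiring about subject's general impression about the stimulation". No version completed by a relative or observer is described.

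**After discharge.** D1.2, step 21: "Patients are advised to call the study team if they experience any untoward side effect before the follow up day". The follow-up visit is at Day 14 ± 4 (Table 2), with vital signs, questionnaire and blood draw.

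**Escalation.** The Definition of Major Response counts a second-degree scalp burn, a seizure, a new unexplained DWI lesion or reduced ADC under the electrode, or discontinuation for one of these. Questionnaire symptoms are not on that list.

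**The concern.** The enrolment rule and the measurement method pull in different directions. One section admits people judged unable to take part in their own consent. Others obtain symptoms such as headache, tingling, itching and burning sensation by asking the subject, and leave it to the subject to raise problems between the stimulation day and the follow-up visit. The plan does not say what happens when the subject cannot do this.

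Two things are at stake. First, the optimal current is meant to balance excitability against tolerability and safety, and D1.3 summarises safety by current group. Pain and discomfort do not count as a major response, so they reach those summaries mainly through the questionnaire, in groups expected to hold three subjects. Second, a burn that shows itself only later, or a seizure at home, is a stopping-rule event that may depend on someone reporting it. The section on potential risks names burns and seizure as possible effects above 2 mA.

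**Working it through.** **1. Group size, reproducing the plan's figures.** D1.1 lists six currents. With three subjects each, 6 × 3 = 18, the number D1.3 expects if no major response occurs. The maximum is 6 × 6 = 36 and the minimum is 3, both as stated. The expected case is therefore three subjects per current.

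**2. Loss from one missing account.** In a group of three, 1/3 of that level's symptom data is lost. If the level is expanded to six, the loss is 1/6.

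**3. Chance that a symptom is seen at all.** Let p be the true rate of a symptom known only by self-report and m the number of subjects able to report. Assuming independence, P(seen at least once) = 1 − (1 − p)^m. The values of p are assumptions.

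| p | m = 3 | m = 2 |
|---|---|---|
| 10% | 1 − 0.9³ = 27% | 1 − 0.9² = 19% |
| 30% | 1 − 0.7³ = 66% | 1 − 0.7² = 51% |

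**4. How often this might arise.** The documents give no share of subjects unable to report. Let q be that share, assumed. The chance of at least one such subject among n is 1 − (1 − q)^n.

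| q | n = 3 | n = 18 |
|---|---|---|
| 1% | 3% | 17% |
| 5% | 14% | 60% |
| 10% | 27% | 85% |
| 20% | 49% | 98% |

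The range is wide, and nothing in the plan narrows it.

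**5. Which stopping-rule events depend on the subject's account.**

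- *DWI lesion or reduced ADC:* no. MRI is repeated within 2 hours after stimulation and read by a blinded reader (MRI Protocol).
- *Burn or seizure during the visit:* no. Staff are present, and pads and scalp temperature are checked mid-session (tDCS Protocol).
- *Burn or seizure evident only after discharge:* possibly. No skin examination is listed among the D1.2 steps after stimulation or at follow-up, and the route before the Day 14 visit is the subject's call.

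**6. Room to recruit.** D5.1 expects 6–8 patients a month to meet the inclusion criteria, against 2–3 a month planned for Aim 1.

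**The case against.** The strongest reply is that the questionnaire does not drive escalation. D1.1 moves up or stops on major responses, which are signs and imaging findings. A reader might infer that a silent subject biases every escalation decision toward tolerable. The documents do not support that: step 5 of the working leaves only post-discharge burns and seizures exposed.

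Three further inferences also fail.

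- *That a subject who cannot consent cannot report.* Understanding a research protocol asks more than saying whether the scalp burned. Some subjects enrolled through a relative will answer adequately.
- *That missing answers will be entered as no symptoms.* The plan does not say how an unanswered item is coded.
- *That one in three subjects will be affected.* This is a possibility the text allows, with no rate behind it.

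There are also partial safeguards. Database and registry candidates are telephoned about their willingness to take part. The protection section says adverse events are recorded at every visit and, under TMS, mentions a daily assessment after each session. A relative who gave consent could telephone.

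These points narrow the concern but do not close it. The consent sentence provides for inability despite the earlier telephone contact. The visit recording and session assessment give no method for a subject who cannot answer, and nothing assigns the relative a reporting role. Consent pages are not in the public copy, so capacity or assent procedures there cannot be judged. The absence of a communication requirement in the eligibility criteria does not depend on them.

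**Conclusion.** The concern holds in a limited form. The plan admits subjects who may be unable to give a reliable account of symptoms, while symptom data and reporting between visits depend largely on that account. For each such subject in a group of three, a third of that current's symptom data is lost. A 30% symptom would then be seen at least once in 51% of cohorts instead of 66%. These percentages assume the symptom rate, independence, and one subject wholly unable to report; they illustrate the loss and do not estimate it. A burn or seizure evident only after discharge may also go unreported before Day 14.

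The point does not show that the maximal tolerable current will be set wrongly. It is worth correcting before Aim 1 enrols because the conflict is between stated rules and the change is short.

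**What to change.** For Aim 1, add an inclusion criterion: *able to give own informed consent and to answer the safety questionnaire*. In D5.5, limit the relative's role to assisting a subject who can understand and respond.

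The cost is a loss of candidates, probably small given the recruitment margin in D5.1 but not quantifiable from the documents. Aim 1 would also support no inference to people who cannot communicate.

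If the sponsor prefers to keep consent by a relative, the less restrictive course is to record each subject's ability to self-report, define structured relative or observer reporting for the questionnaire and the period between visits, and state how unanswered items are handled in the safety summaries. That excludes no one, but an observer cannot fully replace the subject's account of sensations such as tingling or headache.
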